11.2. Blood Volume Limits in Pediatric Patients

The maximum blood volume, which will be collected from pediatric patients over the course of the study, will be based on age and weight and will not exceed those specified in **Table 6**, which was adapted from the Human Subject Protection Program Guidance Document.

Table 6: Maximum Allowable Total Blood Volume Collection Chart

Body Weight	Body Weight	Total blood volume	Maximum allowable volume in a 24-hour period		Total volume collected in a 30-day period	
			2.5% of total blood volume	3% of total blood volume	5% of total blood volume	10% of total blood volume
(kg)	(lbs)	(mL)	(mL)	(mL)	(mL)	(mL)
1	2.2	100	2.5	3	5	10
2	4.4	200	5	6	10	20
3	6.6	240	6	7.2	12	24
4	8.8	320	8	9.6	16	32
5	11	400	10	12	20	40
6	13.2	480	12	14.4	24	48
7	15.4	560	14	16.8	28	56
8	17.6	640	16	19.2	32	64
9	19.8	720	18	21.6	36	72
10	22	800	20	24	40	80
11-15	24-33	880-1200	22-30	26.4-36	44-60	88-120
16-20	35-44	1280-1600	32-40	38.4-48	64-80	128-160
21-25	46-55	1680-2000	42-50	50.4-60	64-100	168-200
26-30	57-66	2080-2400	52-60	62.4-72	104-120	208-240
31-35	68-77	2480-2800	62-70	74.4-84	124-140	248-280
36-40	79-88	2880-3200	72-80	86.4-96	144-160	288-320
41-45	90-99	3280-3600	82-90	98.4-108	164-180	328-360
46-50	101-110	3680-4000	92-100	110.4-120	184-200	368-400
51-55	112-121	4080-4400	102-110	122.4-132	204-220	408-440
56-60	123-132	4480-4800	112-120	134.4-144	224-240	448-480
61-65	134-143	4880-5200	122-130	146.4-156	244-260	488-520
66-70	145-154	5280-5600	132-140	158.4-168	264-280	528-560
71-75	156-165	5680-6000	142-150	170.4-180	284-300	568-600
76-80	167-176	6080-6400	152-160	182.4-192	304-360	608-640
81-85	178-187	6480-6800	162-170	194.4-204	324-340	648-680
86-90	189-198	6880-7200	172-180	206.4-216	344-360	688-720
91-95	200-209	7280-7600	182-190	218.4-228	364-380	728-760
96-100	211-220	7680-8000	192-200	230.4-240	384-400	768-800

Adapted from <http://www.feinsteininstitute.org/wp-content/uploads/2013/02/Maximum-Blood-Draw-Limits.pdf>.[Feinstein Institute 2013]

**ALN-GO1-002 PROTOCOL AMENDMENT 2
SUMMARY OF CHANGES DATED 04 MAY 2020**

**A Phase 2, Multicenter, Open-Label, Extension Study to Evaluate the Long-Term
Administration of ALN-GO1 in Patients with Primary Hyperoxaluria Type 1**

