$>5\times$ to $8\times$ ULN	
• Hold study drug dosing until recovery to $\leq 1.5\times$ ULN or baseline; may resume dosing after discussion with the Medical Monitor• Evaluate the initial elevation in LFT per the following assessments
• Table 4 (all assessments to be performed once)• Hematology, serum chemistry and LFT per Table 3• Coagulation (prothrombin time, partial thromboplastin time, international normalized ratio)• Monitor LFTs at least weekly until ALT and/or AST is declining on 2 consecutive draws, then may decrease monitoring to biweekly• If ALT or AST rises to $>5\times$ ULN following resumption of dosing, permanently discontinue dosing
$>8\times$ ULN	Permanently discontinue dosing after confirmation of the transaminase value at the central laboratory.

Abbreviations: ALT=alanine transaminase; AST=aspartate transaminase; LFT=liver function test(s); ULN=upper limit of normal.

Notes: In addition to these criteria, other assessments or evaluations may be performed per Investigator discretion, as appropriate.

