7.4.7.4. Maximum Blood Volume

The maximum blood volume, which will be collected from pediatric patients over the course of the study, will be based on age and weight and will not exceed those specified in Table 6 from

the Feinstein Institute for Medical Research Human Subject Protection Program Guidance Document (Section 11.2 in the Appendix).[Feinstein Institute 2013]

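### Two 30-day limits in the paediatric blood-volume chart (Protocol Table 6) break the table's own 5% rule: 64 mL should be 84 mL, and 360 mL should be 320 mL

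*Protocol*

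**What the plan says.** Protocol Section 7.4.7.4 states that the maximum volume drawn from paediatric patients "will be based on age and weight and will not exceed those specified in Table 6 from" an outside guidance document. Section 11.2 repeats the commitment, that the volume "will be based on age and weight and will not exceed those specified in" Table 6, and presents the chart as adapted from that source.

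For each weight or weight band, Table 6 gives total blood volume, two limits for a 24-hour period (2.5% and 3%) and two for a 30-day period (5% and 10%). The column at issue is the 30-day one headed "5% of total blood volume". It reads:

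- 21-25 kg, total blood volume 1680-2000 mL: 64-100 mL
- 76-80 kg, total blood volume 6080-6400 mL: 304-360 mL

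Neither section says which of the two 24-hour columns, or which of the two 30-day columns, is the operative limit. The lower of each pair is a natural reading.

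**The concern.** Each limit is a fixed share of blood volume, so it must rise with weight. In the 5% column it does not. A 21 kg child is allowed 64 mL, less than the 80 mL printed for 20 kg. An 80 kg patient is allowed 360 mL, more than the 324 mL printed for 81 kg or the 340 mL printed for 85 kg. Each odd value also appears elsewhere in the same column (64 mL at 16 kg, 360 mL at 90 kg), which looks like a copying slip.

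The protocol binds sites to this chart, so a wrong entry is a wrong safety limit. One error would make a site hold back blood that the 5% rule allows. The other would let it exceed the rule. Both concern 30-day totals, so they matter only where draws repeat within 30 days. The protocol provides for that:

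- **Liver follow-up (Section 6.2.3.1, Table 2).** For transaminases above 5 and up to 8 times the upper limit of normal, the instruction is "Monitor LFTs at least weekly until ALT and/or AST is declining on 2 consecutive draws". For the band above 3 and up to 5 times, monitoring is at least every two weeks.
- **Monthly dosing (Table 1).** Visits fall on Day 1 and Day 29.

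Section 7.4.7 also makes the parallel central-laboratory samples conditional on blood volume, so the limits can affect which samples are sent.

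**Working it through.** **Inputs.** All come from Protocol Table 6: total blood volume (TBV) and the four percentage columns. The table has 10 single-weight rows and 18 bands with two ends each, so 10 + 18 × 2 = 46 weight points and 46 × 4 = 184 percentage values.

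**Step 1: reproduce the table.** Limit = column percentage × TBV. This gives 182 of the 184 values exactly, including every 24-hour value. The two exceptions are:

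| Weight | TBV (mL) | Printed 5% limit (mL) | 0.05 × TBV (mL) | Printed value as share of TBV | Error |
|---|---|---|---|---|---|
| 21 kg | 1680 | 64 | 84 | 64/1680 = 3.81% | −20 mL (−20/84 = −24%) |
| 80 kg | 6400 | 360 | 320 | 360/6400 = 5.63% | +40 mL (+40/320 = +12.5%) |

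**Step 2: is the TBV entry at fault instead?** TBV is 80 mL/kg at every printed weight from 3 kg up. 80 × 21 = 1680 and 80 × 80 = 6400, so both entries are sound.

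**Step 3: cross-check without TBV.** The 5% value should be twice the 2.5% value and half the 10% value. This holds at 44 of the 46 weight points and fails only at these two:

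- 21 kg: 2 × 42 = 84 and 168/2 = 84; printed 64.
- 80 kg: 2 × 160 = 320 and 640/2 = 320; printed 360.

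**Step 4: how far the error spreads within a band.** The chart gives only the band ends. Assume that a site interpolates linearly between them. Printed minus correct is then:

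- 21, 22, 23, 24, 25 kg: −20, −15, −10, −5, 0 mL
- 76, 77, 78, 79, 80 kg: 0, +10, +20, +30, +40 mL

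**Step 5: when could the error bind?** Take the lower limits (2.5% per 24 hours, 5% per 30 days) as governing.

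- At 21 kg, two draw days at the 24-hour cap total 2 × 42 = 84 mL. The 5% rule allows this; the printed 64 mL does not.
- At 80 kg, two such days total 2 × 160 = 320 mL, which is exactly the correct limit. The printed 360 mL loosens the limit only if there is a third draw day, or if the 3% cap applies (2 × 192 = 384 mL).

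**The case against.** The strongest case on the other side accepts the arithmetic and disputes its consequence.

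- **The 10% column may be the operative 30-day limit.** The text does not say. If it is, the limits in these rows (168-200 and 608-640 mL) are correct and neither error reaches a patient. This stands as a limit on the consequence. The 5% column would still print two false values in a chart that sites must follow.
- **Monthly dosing adds little at 80 kg.** Two draw days within the 2.5% cap cannot exceed 320 mL. That is right for two days. However, Table 5 adds a pharmacokinetic blood draw 24 hours after the Day 1 dose, so Day 1, the following day and Day 29 can make three draw days within 30 days. Weekly liver monitoring also gives more than two.
- **The reach is narrow.** The error in the unsafe direction needs a paediatric patient near the top of the 76-80 kg band, in a study of up to 20 patients whose weights are not given. The 64 mL error is protective. Both points stand.
- **The table reveals its own error.** A site can recompute the limit from the heading and the TBV in the same row. True, but a lookup chart is meant to be read, not recalculated.
- **The digits may have been misread from the PDF.** This cannot be wholly excluded, and a look at the printed page settles it. Both rows are otherwise intact and aligned, and each wrong value repeats another entry in its column, which fits a copying slip in the table. The documents do not show whether such a slip came from the cited guidance or from its adaptation. Either way, the protocol adopts the values as its own.

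**Conclusion.** The concern holds, as a minor point. Two of 184 values in a binding paediatric safety chart are wrong by the chart's own rule: 64 mL for 84 mL at 21 kg, and 360 mL for 320 mL at 80 kg. The corrections rest only on figures printed in the same rows and need no outside source. The practical effect depends on the 5% column governing, on a child's weight falling in one of the two bands, and on repeated draws within 30 days. The spread within a band also depends on the assumed linear interpolation. No draw volumes are given, so neither an overdraw nor a dropped sample is demonstrated. All 24-hour limits are correct, and no endpoint or analysis depends on the table.

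**What to change.** In Table 6, 30-day 5% column, print 84-100 mL for 21-25 kg and 304-320 mL for 76-80 kg. As a secondary clarification, add one sentence to Sections 7.4.7.4 and 11.2 naming the 24-hour column and the 30-day column that govern. The cost is two cells in an appendix table and one sentence, with no new procedure.

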1. RATIONALE FOR PROTOCOL AMENDMENT

The primary purpose of this protocol amendment is to incorporate Urgent Safety Measures (USMs) that were communicated to investigators in a Dear Investigator Letter, dated 02 April 2020, to assure the safety of study participants while minimizing risks to study integrity amid the coronavirus 2019 (COVID-19) pandemic. These changes are in line with guidance from both the European Medicines Agency (EMA) and the United States Food and Drug Administration (FDA) on the conduct of clinical trials during the COVID-19 pandemic. [EMA 2020; FDA 2020] The USMs are summarized in Section 1.1.

This protocol amendment also incorporates changes that are not related to USMs. After ongoing review and assessment of the safety data from studies conducted with lumasiran, modifications are designed to enhance patient safety and reduce patient burden regarding blood sampling. These changes are summarized in Section 1.2 and will not be implemented until appropriate Health Authority and Ethics Committee (EC) and/or Institutional Review Board (IRB) approval.

**1.1. Notification of Urgent Safety Measures Due to the Impact of the
COVID-19 Pandemic**

The USM modifications and new procedures are outlined below, and a detailed summary of the USMs is provided in Table 1. These measures were to be adopted immediately by the Investigator site as specified in the Dear Investigator Letter.

• ALN-GO1 dosing outside the study center

Following appropriate training on ALN-GO1 administration, dosing will be permitted at a location other than the study center (eg, at home) by the patient/caregiver at all time points under the oversight of the Investigator and following consultation with the Medical Monitor. This measure is intended to remain in effect only during periods of time when the COVID-19 pandemic impedes the ability of patients to travel to the study site and healthcare professionals to go to patients' homes for dosing.

In order to assure uniform and comprehensive training and to assure compliance with the dosing instructions, the sponsor has prepared both Investigator and caregiver-facing written materials.

• Assessment of adverse events and concomitant medications

In situations where a study visit is unable to be completed (either at the site or offsite by a healthcare professional), the Investigator (or delegate) will verbally contact the patient within the study visit window to assess AEs and concomitant medication use.

• Study visits

Except for assessments with other specified timing requirements, study assessments and dosing can be performed within the expanded window of ± 28 days (was ± 7 days at Month 12 and ± 14 days thereafter).

- **Renal ultrasound and electrocardiogram assessments**

After Month 12, renal ultrasound and ECG assessments may be completed up to 9 months after the intended time point to ensure patient safety, and to the extent possible, maintain study integrity amid travel and other restrictions related to the COVID-19 pandemic.

This expansion of the ECG assessment window is supported by results of a clinical corrected QT interval (QTc) assessment and nonclinical cardiac safety assessment of lumasiran, which demonstrated that lumasiran does not have QTc prolongation properties.

- **Assessments required to be performed in clinic**

Where applicable country and local regulations and infrastructure allow for home healthcare, healthcare may take place at a location other than the clinical trial site to perform study assessments, which may include pregnancy testing (as applicable), collection of blood and urine samples, measurement of vital signs, height and body weight, body system assessment, and preparation and administration of study drug (at the discretion of the Investigator) at all timepoints as specified in the Schedule of Assessments.

- **Full physical examination**

If a visit is conducted offsite (eg, home), a body system assessment can be performed in lieu of a physical examination.

- **Impact of COVID-19 (collection of information)**

Information related to the impact of the COVID-19 pandemic on patient participation in the study will be collected for each patient. Additional information regarding collection of this information, including completion of a new case report form specific to COVID-19, will be provided separately.

This change is implemented to enable analysis of the impact of the COVID-19 global pandemic on clinical trial data.

- **Updates to study administration**

Text was updated to provide clarification of Investigator responsibilities regarding communication of new study information to patients and IRB/IECs.

1.2. Changes Not Related to Urgent Safety Measures

The quality of life (QOL) questionnaire assessment data will not be summarized for this study as no predose data are available from Study ALN-GO1-001 Part B (Study 001B) to determine change from baseline. Additional changes to study conduct (outlined below) will not be implemented until appropriate HA and EC/IRB approval.

- Remove QOL as an exploratory objective and endpoint. The KDQOL for adults ≥ 18 years of age, and the PedsQL; the generic and the end-stage renal disease [ESRD] modules for children < 18 years of age will not be collected after Month 12. QOL data will be listed only but not summarized. These assessments were not performed before the first lumasiran dose in Study 001B; therefore, change from baseline cannot be assessed.
- Clarify coagulation studies assessed in patients with elevated liver enzymes.
- Patients who discontinue pyridoxine (Vitamin B6) therapy during the study will not be required to provide additional blood samples for assessment of pyridoxine levels.
- Clarify assessment time points: performed predose only (ECGs), and at Months 24, 36, 48, and 54 after Month 12 (ECGs and renal ultrasound).

A detailed summary of changes is provided in [Table 2](#). The following changes are not detailed: administrative changes, changes associated with administrative letters (between Amendments 1 and 2), and corrections to typographical errors, punctuation, grammar, abbreviations, and formatting.

2. PROTOCOL AMENDMENT 2 DETAILED SUMMARY OF CHANGES

The primary section(s) of the protocol affected by the changes in Protocol Amendment 2 are indicated. The corresponding text has been revised throughout the protocol. Deleted text is indicated by ~~strikeout~~; added text is indicated by **bold** font.

Table 1: Urgent Safety Measures COVID-19-related Changes to be Adopted Immediately

Purpose: Expand the use of offsite administration to include ALN-GO1 dosing by the caregiver and provide additional instructions on self administration, and preparation, handling, and storage of the study drug.

The primary change occurs in Section 6.2.2, Dose and Administration

Revised text: Study drug will be administered under the supervision of the Investigator or designee. **Dosing will be permitted at a location other than the study center (eg, the patient's home) by a healthcare professional with oversight of the Investigator at all time points, provided the patient has tolerated ALN-GO1 administered in the clinic.**

If the patient is unable to come to the study site, and a visit by a healthcare professional is not possible due to circumstances related to the COVID-19 pandemic, ALN-GO1 may be administered by the patient or the caregiver under the oversight of the Investigator, and following consultation with the Medical Monitor, as allowed by applicable country and local regulations. In such cases, the patient or caregiver must receive appropriate training on ALN-GO1 administration prior to dosing.

Administration by a patient or caregiver is intended to remain in effect only during periods of time when the COVID-19 pandemic impedes the ability of patients to travel to the study site and healthcare professionals to go to the patients' homes for dosing.

In addition, instructions and procedures related to administration of ALN-GO1 by a patient or caregiver will be provided in the Patient/Caregiver Storage and Administration Instructions.

Section(s) also reflecting this change:

- Section 6.2.4, Preparation, Handling, Storage

Purpose: Allow additional offsite assessments

The primary change occurs in Section 7, Study Assessments.

Revised text: **Where applicable country and local regulations and infrastructure allow for home healthcare**, healthcare may take place at a location other than the clinical trial site to perform study assessments, which may include pregnancy testing (as applicable), collection of blood and urine samples, measurement of vital signs, **height and body weight, body system assessment**,

and preparation and administration of study drug (at the discretion of the Investigator) at all timepoints **as specified in the Schedule of Assessments**.

Section(s) also reflecting this change:

- Section 7.4.3, Physical Examination
- Section 7.4.7.2, Pregnancy Testing

Purpose: Expand the study visit window.

The primary change occurs in Table 1, Schedule of Assessments.

Revised text: The study site visit window was changed from ± 14 days to ± 28 days through the end of the study.

Purpose: Expand the window for body weight measurement.

The primary change occurs in notes for Table 1, Schedule of Assessments.

Revised text: **Body weight must be obtained within 4 months prior to dosing.**

Section(s) also reflecting this change:

- Section 6.2.2, Dose and Administration

Purpose: Expand study assessment windows for ECGs and renal ultrasound.

The primary change occurs in Section 7.4.4, Electrocardiogram

Revised (added) text: **During periods of time when the COVID-19 pandemic impedes the ability of patients to travel to the study site, ECGs may be completed up to 9 months after the intended timepoint.**

Section(s) also reflecting this change:

- Section 7.4.6, Renal Ultrasound

Purpose: Allow continual assessments of AEs and concomitant medications via remote contact.

The primary change occurs in Table 1, Schedule of Assessments (notes)

Revised (added) text: **• In situations where a study visit is unable to be completed (either at the site or offsite by a healthcare professional), the Investigator (or delegate) will verbally contact the patient within the study visit window to assess concomitant medications and adverse events.**

Purpose: Collect information related to the impact of the COVID-19 pandemic on patient participation in the study.

The primary change occurs in Section 7.4.9, COVID-19 Data Collection

Revised text: **Information on the coronavirus disease 2019 (COVID-19) infection status of the patient, if known, and other information on the impact of the COVID-19 pandemic on the patient's participation in the study will be collected.**

Section(s) also reflecting this change:

- Section 8.2, Statistical Methodology

Purpose: Revise and update informed consent instructions.

The primary change occurs in Section 9.1.1, Informed Consent

Revised (added) text: **The Investigator will inform the patient/legal guardian if new information becomes available that may be relevant to the patient's/legal guardian's willingness to continue participation in the study. Communication of this information should be documented.**

Purpose: Revise and update ethical review instructions.

The primary change occurs in Section 9.1.2, Ethical Review

Revised (added) text: **In addition, the IRB or IEC must approve all advertising used to recruit patients for the study (except those that support the need to remove an apparent immediate hazard to the patient).**

Table 2: Changes Not Related to Urgent Safety Measures to be Implemented After Health Authority and Ethics Committee(EC)/Institutional Review Board (IRB) Approval, where applicable

Purpose: Remove QOL as an exploratory study objective and stop collection of the QOL (KDQOL and PedsQL) questionnaires after Month 12.

The primary change occurs in Section 2.3, Exploratory Objectives

- ~~Characterize quality of life~~

Sections also reflecting this change:

- Section 3.3, Exploratory Endpoints
- Section 7.5.1, Quality of Life
- Section 8.2.9, Other Analyses
- Synopsis, Exploratory Objectives; Exploratory Endpoints
- Table 1, Schedule of Assessments

Purpose: To clarify coagulation parameters.

The primary change occurs in Section 6.2.3, Table 2, Monitoring and Dosing Rules for Asymptomatic Patients with Confirmed Isolated Elevations of ALT and/or AST >3 x ULN, with no Alternative Cause

Revised text: • Hematology, serum chemistry, ~~and LFT, and coagulation~~ per Table 3
• **Coagulation (prothrombin time, partial thromboplastin time, international normalized ratio)**

Section(s) also reflecting this change:

- Section 7.4.7.3, Additional Liver Function Assessments

Purpose: Remove the requirement for measurement of pyridoxine after discontinuation of pyridoxine therapy.

The primary change occurs in Section 6.3, Concomitant Medications.

Revised (deleted) text: ~~If pyridoxine therapy is discontinued, pyridoxine levels should be assessed for at least the next 2 study visits.~~

Section(s) also reflecting this change:

- Table 1, Schedule of Assessments

Purpose: Clarify the timing of 12-lead ECGs and renal ultrasounds.

The primary change occurs in Table 1, Schedule of Assessments

Revised text: After Month 12, ECGs and renal ultrasounds will be performed at ~~X (Q12M)~~ **Months 24, 36, 48, and 54 only.**

Section(s) also reflecting this change:

- Section 7.4.4, Electrocardiogram (remove the 2 to 4 hours after dosing timepoint)

Purpose: Clarify that vital signs will be measured in the supine or seated position.

The primary change occurs in Section 7.4.1, Vital Signs

Revised text: Vital signs will be measured in the supine **or seated** position, after the patient has rested comfortably for approximately 10 minutes.

